## Treatment Groups and Duration

Subjects with CLE that meet the entry criteria at the time of screening will be enrolled into two treatment arms dependent on the number of active lesions they present with.

Group A: Patients with fewer than 2 active lesions will be enrolled into group A and exposed to PV for 3 consecutive days. Patients with Lupus Erythematosus Tumidus (LET) can be enrolled into Group A only, and can present with any number of lesions, so long as the existing lesions are not in the areas designated for photoprovocation. Patients will be assessed for the development of lesions up to 14 days from the first PV. Patients that develop PV lesions at any time during this period, as determined by the local investigative team, will receive 1% strength GSK2646264 on 1 lesion and placebo on 1 lesion daily and either 1% strength GSK2646264 or placebo on an area of uninvolved skin, for skin PK of study drug, for 28 days.

Group B: Patients that have a minimum of 2 active existing CLE lesions as determined by the investigators will be enrolled into group B and have one lesion treated with 1% GSK2646264 and 1 lesion with placebo.

A completed patient will be defined as a subject who receives at least 25 days of study drug and completes the end of treatment biopsy (at day 28) and assessment. Thereafter patients will be followed for 28 days or until complete resolution of induced PV lesions, as determined by the investigator.

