
Group B will commence in parallel and recruit approximately 15 patients with a minimum of 2 active CLE lesions within the same anatomical area. At the day-5 to day -3 visit the two chosen lesions will be labelled based on size F (the larger) and G (the smaller). Pre-dose biopsies will be taken from both of the lesions (F+G) and an additional biopsy (H) from uninvolved skin from the same anatomical area will also be taken. The patients will be randomised 2-4 days later to allow for healing of the biopsies (F+G) and one lesion will then be treated with 1% GSK2646264 and the other with placebo once daily for 28 days. Biopsies will be obtained post-treatment from both treated CLE lesion (F+G). A completed patient will be defined as a patient who receives at least 25 days of study drug and completes the end of treatment biopsy (day 28) and assessment.

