## 7.1.3. Group B

Procedure	Screening (up to Day -28)	Day -5 to -3	Day 1	Day 2 to Day 13	Day 14	Day 15 to Day 20	Day 21 to Day 27	Day 28	Day 29 to 42	Follow-up (between Day 43 to Day 56) a	All procedures listed to also be conducted if a subject decides to prematurely withdraw/discontinue
Informed Consent	X										
Inc/Exc criteria assessment	X										
Demography	X										
Pregnancy Test (women)	X		X		X				X	Pregnancy testing to be performed at Screening, on Day 1 (pre-dose), Day 14 (pre-dose) and once during follow-up, with day recorded	
TSH, free T4, freeT3	X		X		X				X		
Vital Signs	X	X			X			X			
Safety Lab Samples (clin chem ,haematol, Urinalysis)	X	X	X		X			X	X	On days of dosing samples should be taken predose	
Full Physical Exam	X								X		
Brief Physical Exam			X							Assessment to be performed pre-dose	
12-lead ECG	X		X		X				X	On days of dosing assessments should be performed predose	
SLE clinical assessment	X		X					X	X	On days of dosing assessment as defined by the investigator to be performed pre-dose .	
ANA, anti-dsDNA antibodies, anti-Ro and anti-La antibodies, HIV, Hep B, Hep C, FSH, Drug screen	X										
Lesion selection		X								Refer to Section 4.1 and	

Procedure	Screening (up to Day -28)	Day -5 to -3	Day 1	Day 2 to Day 13	Day 14	Day 15 to Day 20	Day 21 to Day 27	Day 28	Day 29 to 42	Follow-up (between Day 43 to Day 56) a	a All procedures listed to also be conducted if a subject decides to prematurely withdraw/discontinue
											Section 6.1
Skin Biopsies		X b						X b			b 2 to 4 days healing time will be allowed prior to randomisation and the first dose. Day 28 biopsies will be taken 4 hours post-dose
Clinical score			X		X			X			
Local tolerability Assessment			X	X	X	X	X	X	X		Assessments to be performed pre-dose and up to one hour following dosing on days of dosing
Dosing			X	X	X	X	X	X			Once daily
Randomisation			X								Pre-dose

Procedure	Screening (up to Day -28)	Day -5 to -3	Day 1	Day 2 to Day 13	Day 14	Day 15 to Day 20	Day 21 to Day 27	Day 28	Day 29 to 42	Follow-up (between Day 43 to Day 56) a	a All procedures listed to also be conducted if a subject decides to prematurely withdraw/discontinue

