11.3.3. Safety

ECG Parameters

RR Interval

- IF RR interval (msec) is not provided directly, then RR can be derived as :
 - [1] If QTcB is machine read & QTcF is not provided, then :

$$RR = \left[\left(\frac{QT}{QTcB} \right)^2 \right] * 1000$$

- [2] If QTcF is machine read and QTcB is not provided, then:

$$RR = \left[\left(\frac{QT}{QTcF} \right)^3 \right] * 1000$$

- If ECGs are manually read, the RR value preceding the measurement QT interval should be a collected value THEN do not derive.

Corrected QT Intervals

- When not entered directly in the eCRF, corrected QT intervals by Bazett's (QTcB) and Fredericia's (QTcF) formulas will be calculated, in msec, depending on the availability of other measurements.
- IF RR interval (msec) is provided then missing QTcB and/or QTcF will be derived as :

$$QTcB = \frac{QT}{\sqrt{\frac{RR}{1000}}} \qquad QTcF = \frac{QT}{\sqrt[3]{\frac{RR}{1000}}}$$

Laboratory Parameters

- If a laboratory value which is expected to have a numeric value for summary purposes, has a non-detectable level reported in the database, where the numeric value is missing, but typically a character value starting with '<x' or '>x' (or indicated as less than x or greater than x in the comment field) is present, the number of significant digits in the observed values will be used to determine how much to add or subtract in order to impute the corresponding numeric value.
 - Example 1: 2 Significant Digits = '< x ' becomes x - 0.01
 - Example 2: 1 Significant Digit = '> x' becomes x + 0.1
 - Example 3: 0 Significant Digits = '< x' becomes x - 1

Tolerability score

Tolerability will be assessed with the skin irritation scoring system for Part A and B of study, where the score consists of a numeric score according to the dermal response scoring i), and a letter according to the other effects scoring ii), as follows:

i) Dermal response scoring:

0 = no evidence of irritation

1 = minimal erythema, barely perceptible (pink)

2 = moderate erythema (definite redness), readily visible; minimal edema or minimal papular response

3 = strong erythema (intense redness), or erythema and papules

4 = definite edema

5 = erythema, edema, and papules

6 = vesicular eruption

7 = strong reaction spreading beyond test site

ii) Other effects:

Z = no other effect

A = slight glazed appearance

B = marked glazing

C = glazing with peeling and cracking

F = glazing with fissures

G = film of dried serous exudate covering all or part of the patch site

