H = small petechial erosions and/or scabs

For each skin assessment, letter grade will be converted to numeric values as below:

A=0, Z=0, B=1, C=2, F=3, G=3, H=3.

A combined score for each subject will be calculated by adding all numeric and letter scores

The Skin Irritation Score for will be calculated for each subject at each timepoint and for each body part.

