ECG					
2.13.	Safety	EG1	Summary of ECG Findings (Group B-Natural Lesions)	Treatment columns will be replaced by one 'Part B' column	SAC
2.14.	Safety	CP_EG11	Summary of Maximum Emergent QTc Values by Category (Group B-Natural Lesions)	Treatment columns will be replaced by one 'Part B' column	SAC
2.15.	Safety	EG2	Summary of Change from Baseline in ECG Values by Visit (Group B-Natural Lesions)	Note: IDSL shell in development. Includes Baseline values. Treatment columns will be replaced by one 'Part B' column	SAC
2.16.	Safety	CP_EG12	Summary of Maximum Change from Baseline in QTc Values by Category (Group B-Natural Lesions)	Treatment columns will be replaced by one 'Part B' column	SAC
Vital Signs					
2.17.	Safety	VS1	Summary of Change from Baseline in Vital Signs by Visit (Group B-Natural Lesions)	Treatment column will not be displayed.	SAC
2.18.	Safety	VS3	Summary of Emergent Vital Signs Results Relative to Normal Range (Group B-Natural Lesions)	Treatment columns will be replaced by one 'Part B' column	SAC
Local Tolerability					
2.19.	Safety	SAFE_T1	Summary (Absolute and Change from Baseline) of Mean irritation score assessment – (Group B-Natural Lesions)		SAC
2.20.	Safety	SAFE_T2	Assessment of Maximum Dermal Reactions and Response (Group B-Natural Lesions)		SAC

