11.9. Appendix 9: Example Mock Shells for Data Displays

Example : SAFE_T1 Page x of y
 Protocol : 204860
 Population : Safety

Table x.xx

Summary (Absolute and Change from Baseline) of Mean irritation score assessment

Summary: Mean Irritation score (Absolute)

Treatment	Time		n	Mean	S.D	Min	Median	Max
		N						
Placebo	X	X	X	xxx.x	xx.xx	xxx	xxx	xxx
	X	X	X	xxx.x	xx.xx	xxx	xxx	xxx
	X	X	X	xxx.x	xx.xx	xxx	xxx	xxx
.								
GSK2646264	X	X	X	xxx.x	xx.xx	xxx	xxx	xxx
	X	X	X	xxx.x	xx.xx	xxx	xxx	xxx
	X	X	X	xxx.x	xx.xx	xxx	xxx	xxx
.								

Example : SAFE_T2
 Protocol : 204860
 Population : Safety

Page x of y

Table x.xx
 Summary of Tolerability: Maximum Dermal Response and Maximum Other Dermal Effects

Assessment	Statistic	GSK2646264 (N = XX)	Placebo (N = XX)
Maximum Dermal Response	0	n (%)	XX (XX.XX)
	1	n (%)	XX (XX.XX)
	2	n (%)	XX (XX.XX)
	-	-	-
	7	n (%)	XX (XX.XX)
Maximum Other Dermal Effects	Z	n (%)	XX (XX.XX)
	A	n (%)	XX (XX.XX)
	B	n (%)	XX (XX.XX)

	H	n (%)	XX (XX.XX)

Note: NA = not applicable

Note: Treatment is GSK2646264 1% and matching Placebo, on the respective body surface area, one side each.

Note: Dermal Response: 0 = no evidence of irritation, 1 = minimal erythema, barely perceptible (pink), 2 = moderate erythema (definite redness), readily visible; minimal edema or minimal papular response, 3 = strong erythema (intense redness), or erythema and papules, 4 = definite edema, 5 = erythema, edema, and papules, 6 = vesicular eruption, 7 = strong reaction spreading beyond test site.

Note: Other Dermal Effects: Z = no other effect, A = slight glazed appearance, B = marked glazing, C = glazing with peeling and cracking, F = glazing with fissures, G = film of dried serous exudate covering all or part of the patch site, H = small petechial erosions and/or scabs.

CONFIDENTIAL

204860

Example : SAFE_T3
Protocol : 204860
Population : Safety

Table x.xx
Summary of Type of CLE (Group B-Natural Lesions)

CLE type	N=XX
Chronic	n (%)
Acute	n (%)
Sub-acute	n (%)
LTE	n (%)

Example : PD_T1
 Protocol : 204860
 Population : Safety

Page 1 of n

Table Summary of [RCLASI/PD endpoints]
 [Insert Title]

Type of CLE	Treatment	N	Visit	n	Mean	95% CI of Mean	SD	Median	Min.	Max.
Sub-Acute	GSK2646264	X	Day 1	24	xxxxx.xx	(xxxxx.xx, xxxx.xx)	xx.xx	xxxx.x	xxxx	xxxx
			Predose							
			Day 14	24	xxxxx.xx	(xxxxx.xx, xxxx.xx)	xx.xx	xxxx.x	xxxx	xxxx
	Placebo	X	Day 28	23	xxxxx.xx	(xxxxx.xx, xxxx.xx)	xx.xx	xxxx.x	xxxx	xxxx

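### Table 2.20 reports only the absolute maximum local tolerability grade, so it does not separate reactions arising on treatment from disease signs and biopsy wounds present before the first dose

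*SAP*

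**What the plan says.** SAP Section 11.8.5 lists Table 2.20 as "Assessment of Maximum Dermal Reactions and Response (Group B-Natural Lesions", with an empty programming note and shell SAFE_T2. The shell (SAP Section 11.9) is titled "Summary of Tolerability: Maximum Dermal Response and Maximum Other Dermal Effects". It gives n (%) at each dermal grade from 0 to 7 and each letter from Z to H, in a GSK2646264 column and a Placebo column. Its footnote reads "Treatment is GSK2646264 1% and matching Placebo, on the respective body surface area, one side each". There is no baseline row, shift or change. SAP Table 5 (Section 7.1.3) agrees: the dermal response and other-effects grades are marked for absolute display only.

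The scale (Protocol Section 5.4.2, SAP Section 11.3.3) includes "3 = strong erythema (intense redness), or erythema and papules" and "H = small petechial erosions and/or scabs", along with oedema, papules and dried exudate.

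Group B enrols patients "with a minimum of 2 active CLE lesions within the same anatomical area" (Protocol Section 4.1). Both study lesions have a pre-dose punch biopsy, 4 mm by Protocol Section 7.5.2, with 2-4 days allowed for healing before randomisation and the first dose.

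On tolerability scoring, the Group B schedule (Protocol Section 7.1.3) says "Assessments to be performed pre-dose and up to one hour following dosing on days of dosing". It marks scores from Day 1 through Day 28 and again in Day 29 to 42. The second biopsy is taken on Day 28, four hours after the dose.

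The Group B baseline table in SAP Section 11.2.2.1 covers vital signs, laboratory samples, ECG, biopsies, RCLASI and plasma PK. It has no row for local tolerability.

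**The concern.** A maximum grade on treated skin is normally read as the worst reaction to the product. Here the skin is diseased and recently wounded before any cream is applied. Erythema and oedema are also components of the modified RCLASI activity score (SAP Section 11.3.4), and a healing punch site can plausibly give a scab, which is letter H. A lesion can therefore reach a high row of Table 2.20 with no reaction to the cream.

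The window for the maximum is also open. The SAP does not say whether the Day 1 pre-dose score counts, or whether the Day 29 to 42 scores do. If the later scores count, a scab from the Day 28 biopsy could set a lesion's maximum.

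The table matters because little else in the safety output is split by treatment. Every subject receives both creams, so adverse events are shown as totals, and laboratory, ECG and vital-sign tables drop the treatment columns. Tables 2.19 and 2.20 are the only safety tables that compare the two creams, and 2.20 is the only one by grade. The primary endpoint text does not name this scale, but the SAP places it under its primary statistical analyses.

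**Working it through.** **No figure to reproduce.** The plan states none for Table 2.20. The protocol's Group B illustration (Section 9.2.1) does reproduce: Beta(2, 15) has a 95% interval of 0.016 to 0.302, stated as 0.02 to 0.30. It treats a count out of 15 as an incidence, and that is the reading that Table 2.20 does not support.

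**Inputs**
- From the documents: n = 15 lesions per column (planned Group B size); lesions F and G randomised 1:1 within subject (Protocol Section 6.1).
- Assumed, because the documents give no value:
  - b, the share of lesions already at or above a given grade before dosing, equal in expectation on both lesions;
  - r, the share of the remaining active-treated lesions that the cream pushes to that grade;
  - no new worsening on placebo;
  - rho, the within-subject correlation of starting status.

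**Step 1: what the columns show.** Active = b + (1 - b) x r. Placebo = b. For example, at b = 0.8 and r = 0.20, active = 0.80 + 0.20 x 0.20 = 0.84.

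| b | Active, r = 0.20 | Active, r = 0.40 | Placebo | Lesions below the grade at baseline, 15 x (1 - b) |
|---|---|---|---|---|
| 0 | 20% | 40% | 0% | 15 |
| 0.2 | 36% | 52% | 20% | 12 |
| 0.5 | 60% | 70% | 50% | 7.5 |
| 0.8 | 84% | 88% | 80% | 3 |
| 1 | 100% | 100% | 100% | 0 |

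The active column overstates r whenever b > 0, and the placebo column shows b although no placebo lesion reacted. The difference, (1 - b) x r, keeps its direction and disappears only at b = 1.

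**Step 2: what a baseline comparison adds.** Counting lesions that newly reach the grade, over all 15, gives (1 - b) x r on active and 0 on placebo. The difference is the same as in Step 1. Correction alone recovers no hidden effect; it removes b from both columns. Dividing by the lesions below the grade at baseline returns r, on the reduced number in the last column.

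**Step 3: chance imbalance.** Randomisation balances b only in expectation. The SD of the difference in starting share is sqrt(2 x b x (1 - b) x (1 - rho) / 15). At b = 0.5:
- rho = 0: sqrt(0.50 / 15) = 0.18
- rho = 0.5: sqrt(0.25 / 15) = 0.13

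On-treatment differences at b = 0.5 are 10 points (r = 0.20) and 20 points (r = 0.40). An imbalance of one SD is of the same order, and Table 2.20 alone cannot reveal it.

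**Step 4: the other displays.** Table 2.19 gives absolute values and change from baseline for the combined score, which adds the dermal number to a converted letter (F, G and H all become 3). A change from Z to H therefore adds 3, the same as a rise of three dermal grades. A mean of that score cannot show how many lesions worsened or to what grade. Listing 35 shows grades by visit and the change in combined score, but it is not a summary.

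**The case against.** The strongest reply is that the design already supplies the control. The placebo lesion is in the same subject and anatomical area, is also active and biopsied, and is allocated at random. Disease and biopsy add the same expected background to both columns. This stands: the contrast is informative.

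Baseline-corrected tolerability is also planned. Table 2.19 and Listing 35 report change from baseline, and SAP Section 11.2.2.2 requires the baseline definition in a footnote. This stands too, except that no tolerability baseline is defined for that footnote to state.

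The absolute maximum has its own use, since the tolerability criteria in Protocol Section 5.4.1 are written in absolute grades. That is a reason to keep it, not to leave it alone.

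A reader might infer that Table 2.20 measures disease and scabs rather than tolerability, or that lesions start so high that irritation cannot show. The documents do not support this. They give no distribution of pre-dose grades and set no minimum redness for an active lesion. The dermal scale runs to 7 and every grade has its own row, so a lesion that starts at 3 and worsens to 5 changes rows. A ceiling is more plausible for the letter scale, where a scab already scores H, but its frequency is unknown.

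**Conclusion.** The point holds as a limit on what Table 2.20 can show. It does not separate reactions arising on treatment from disease signs and biopsy effects, and neither column is a reaction rate. The gap lies in one descriptive table and one missing baseline definition, not in the whole tolerability plan. No formal safety comparison depends on it.

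Its size cannot be fixed from the documents. It runs from nothing, if no lesion starts at the grade in question, to complete loss of the contrast at that grade, if every lesion does. The illustrations rest on assumed b, r and rho and on the planned 15 pairs. The SAP refers to a small number of patients; with fewer pairs, chance imbalance would be larger. That active lesions already show redness is a reasonable inference, not a stated fact.

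The change is worth making because it uses scores already scheduled and follows the SAP's own practice: maximum QTc (Table 2.14) is paired with maximum change from baseline (Table 2.16). Table 2.20 has no such partner by grade.

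**What to change.** Before the final database freeze:

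1. In SAP Section 11.2.2.1, add a Group B row for local tolerability with the Day 1 pre-dose score as baseline, separately for each lesion. This also settles the baseline for Table 2.19.
2. In the programming note for Table 2.20, restrict the maximum to post-dose scores and state whether the Day 29 to 42 scores, taken after the Day 28 biopsy, count.
3. In shell SAFE_T2, add a block by treatment showing the shift from baseline grade to maximum post-dose grade, for the dermal response and the other effects. Use the number of lesions below each grade at baseline as the denominator, and print that number.
4. Keep the absolute maximum as it is, and mark change from baseline for these grades in SAP Table 5.

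The cost is SAP wording and one block in an existing table, with no new assessments. Where few lesions start below a grade, the share will rest on few lesions; printing the denominator makes that visible.

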11.8.6. Efficacy Tables

Efficacy: Tables					
No.	Population	IDSL / TST ID / Example Shell	Title	Programming Notes	Deliverable [Priority]
RCLASI					
3.1.	Safety	PD_T1	Summary of RCLASI and components (Absolute and Change from Baseline) (Group B-Natural Lesions)	Page by score type (e.g. component/final) Include absolute and change from baseline. First variable for Type of CLE – include All. Include footnote for derivation (see Section 11.3.4)	SAC

11.8.7. Efficacy Figures

Efficacy: Figures					
No.	Population	IDSL / TST ID / Example Shell	Title	Programming Notes	Deliverable [Priority]
RCLASI					
3.1.	Safety	PD_F1	Individual profile plots of RCLASI and components (Group B-Natural Lesions)	Page by score type (e.g. component/final) Column panel by treatment group Symbol by subject Id. Line pattern by CLE type. Include footnote for derivation (see Section 11.3.4)	SAC
3.2.	Safety	PD_F2	Summary of Mean (\pm SE) in RCLASI and components (Group B-Natural Lesions)	Panel by CLE type (include All). Include footnote for derivation (see Section 11.3.4)	SAC

11.8.8. Pharmacokinetic Tables

Pharmacokinetic : Tables					
No.	Population	IDSL / TST ID / Example Shell	Title	Programming Notes	Deliverable [Priority]
4.1.	PK	PKPT1	Summary of Serum GSK2646264 Pharmacokinetic concentrations versus time by actual dose (Group B-Natural Lesions)		SAC
4.2.	PK	PKPT1	Summary of Derived Serum GSK2646264 Pharmacokinetic Parameters by actual dose (Group B-Natural Lesions)		SAC
4.3.	PK	PKPT1	Summary of Log-Transformed Derived Serum GSK2646264 Pharmacokinetic Parameters by actual dose (Group B-Natural Lesions)		SAC

11.8.9. Pharmacokinetic Figures

Pharmacokinetic : Figures					
No.	Population	IDSL / TST ID / Example Shell	Title	Programming Notes	Deliverable [Priority]
4.1.	PK	PKCF1P	Individual GSK2646264 Plasma Concentration-Time Plot by Subject (Linear and Semi-Log) (Group B-Natural Lesions)	Refer Table1 treatment description table 1.X-axis display actual relative time 2.Include line for LLQ along with footnote defining LLQ value 3.Include values below LLQ	SAC
4.2.	PK	PKCF2	Mean (\pm SD) Plasma GSK2646264 Concentration-Time Plots (Linear and Semi-log) (Group B-Natural Lesions)	1.Refer Table 1 treatment description table 2. Include the full SD bars i.e.(not just the +ve SD) at each time point. 3. X-axis displays planned relative time 4. Include line for LLQ along with footnote defining LLQ value.	SAC
4.3.	PK	PKCF3	Median (Range) Plasma GSK2646264 Concentration-Time Plot (Linear and Semi-log) (Group B-Natural Lesions)	1.Refer Table 1 treatment description table 2. X-axis displays planned relative time 3. Include line for LLQ along with footnote defining LLQ value. 4. Combine data per dose group; i.e. no distinction of ADA status	SAC

11.8.10. Pharmacodynamic Tables

Pharmacodynamic (and or Biomarker) : Tables					
No.	Population	IDSL / TST ID / Example Shell	Title	Programming Notes	Deliverable [Priority]
IFN mRNA signature					
5.1.	Safety	PD2	Summary of mRNA Expression of Inflammatory Gene Transcripts in Biopsy (Group B-Natural Lesions)	Summary by treatment group (Placebo, GSK2646264 and uninvolved skin) First variable for Type of CLE – include All. See Section 11.3.5 for list of genes and probe-sets to be summarised	SAC
5.2.	Safety	PD_T2	Summary of Adjusted Mean and Fold Changes in mRNA Expression of Inflammatory Gene Transcripts in Biopsies (Group B-Natural Lesions)	Summary by treatment group (Placebo and GSK2646264) See Section 11.3.5 for list of genes and probe-sets to be analysed Footnote: 'Comparison to placebo fold change' is the fold change on GSK2646264 relative to placebo in log ₂ intensity at day 28.'	SAC
5.3.	Safety	PD_T3	Summary of Adjusted Mean and Fold Changes in mRNA Expression of Inflammatory Gene Transcripts in Biopsies by Skin Type (Group B-Natural Lesions)	Summary by skin type See Section 11.3.5 for list of genes and probe-sets to be analysed Footnote: 'Comparison to uninvolved fold change' is the fold change on GSK2646264 relative to placebo in log ₂ intensity.'	SAC

Pharmacodynamic (and or Biomarker) : Tables					
No.	Population	IDSL / TST ID / Example Shell	Title	Programming Notes	Deliverable [Priority]
Other biomarkers					
5.4.	Safety	PD_T1	Summary of Cell Markers from Immunohistochemistry (Absolute and Change from baseline) (Group B-Natural Lesions)	Summary by lesion type (Placebo, GSK2646264 and uninvolved skin). Replace treatment title with 'Lesion type' First variable for Type of CLE – include All.	SAC
5.5.	Safety	PD_T1	Summary of Histopathology score and components in skin biopsies (Absolute and Change from baseline) (Group B-Natural Lesions)	Page by score type – e.g final score then component score summaries Summary by lesion type (Placebo, GSK2646264 and uninvolved skin). Include change from baseline column where applicable. Replace treatment title with 'Lesion type' First variable for Type of CLE – include All.	SAC

